5.3 Method for Assigning Subjects to Treatment Groups

Each group (or dose level) will enroll and after 4 weeks of follow up of 3 patients treated with ixazomib at a particular dose will be reviewed for safety by DSMB before initiating enrollment into the next group (or dose level). All patients in the current cohort must have completed 4 weeks and the cohort's data reviewed by the by the Safety Monitoring Committee before patients in the next cohort can receive drug. Patients from the next cohort may complete the first two visits prior to DSMB review of earlier cohorts.

Dose limiting toxicities are defined in Section 6.17 Table 2. After all the subjects in each dosing group has completed Cycle 1 of ixazomib, the DSMB may recommend:

- (i) Proceed to next dose level, or
- (ii) Terminate trial, or
- (iii) Enroll a replacement subject for a withdrawn subject, or
- (iv) Add 5 more patients at previous dose group (maximum tolerated dose). The maximum tolerated dose is that level where no more than 0 out of 3 patients experience dose limiting toxicity.

If no DLT are observed in 3 subjects, the next dosing level will be initiated.

After DSMB review of the 4 mg dosing level, if no DLT are observed, the DSMB may recommend:

- (i) Terminating the trial
- (ii) Enroll 5 more patients at the maximum tolerated dose.

The NNRTIs etravirine and efavirenz are moderate CYP3A enzyme inducers and have potential to decrease systemic exposure to ixazomib. That possibility will be explored by measuring trough ixazomib levels in all patients and comparing ixazomib concentrations in patients on different ART regimens. The DSMB will have to consider the number of patients treated with NNRTIs in a particular group as the safety profile of a group may be underestimated if the majority of patients are treated with NNRTIs as part of their ARV regimen.

Additional data review by the DSMB will occur after Day 84 for each dosing cohort. At this time, the DSMB may recommend:

[figure not shown]
- (i) Proceed to uninterrupted weekly dosing on days 1, 8, 15 and 22 of a 28 day cycle, or
- (ii) Continue previous dosing on days 1, 8, and 15 of a 28 day cycle, or
- (iii) Enroll a replacement subject for a withdrawn subject, or
- (iv) Terminate dosing.

This determination will be made on an individual participant basis, and not a dosing cohort basis, and will be made based on the presence or absence of adverse drug effects that do not meet the definition of dose related toxicities.

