Screening for peripheral neuropathy will occur at baseline (for study exclusion), and at each study visit (for safety monitoring), by administration of the European Organization for Research and Treatment of Cancer QLQ-CIPN20 Questionnaire. The 20-item CIPN-specific questionnaire which includes three scales assessing sensory (9 items), motor (8 items), and autonomic (3 items) symptoms and functioning with each item formatted the same as items of the EORTC QLQ-C30. It was developed to be used in conjunction with the EORTC QLQ-C30 following the EORTC guidelines for module development (15911236). The EORTC QLQ-CIPN20 has been tested in cancer patients receiving a variety of chemotherapies and has been shown to have internal consistency reliability based on Cronbach's alpha coefficients of 0.82, 0.73, and 0.76 for the three scales, respectively (PMID 23543373). The questions that comprise the QLQ-CIPN20 are listed in Appendix II. Any affirmative answer to questions in the QLQ-CIPN20 will trigger a further clinical assessment, and grading of suspected peripheral neuropathy according to the (CTCAE) Version 4.0 scale (Appendix I). Further clinical assessment of suspected peripheral neuropathy will be referred to a qualified physician in the area of drug-induced peripheral neuropathy.

The following toxicities will be considered to be dose limiting toxicities:

- Any \geq Grade 4 toxicity
- Any Grade 3 AE (except if there is clear evidence that it is not ixazomib related – i.e. a plausible alternative reason).
- Any \geq Grade 1 peripheral neuropathy (PN)

Specific management of toxicities in individual participants is discussed below.

Study related biology assays for the secondary outcomes include:

- CD4 T cell count, CD8 T cell count and CD4/CD8 ratio – by routine clinical flow cytometry (Mayo Medical Labs).
- Plasma HIV RNA viral load – by routine clinical RT-qPCR (Mayo Medical Labs).
- HIV Proviral DNA – by clinical qPCR (Mayo Medical Labs)
- Cell associated HIV DNA by digital droplet PCR – Peripheral blood CD4 T cells will be isolated from baseline and post-treatment leukapheresis samples by magnetic bead negative selection. Cell associated HIV DNA will be quantified by digital droplet PCR using RainDance™ ddPCR system ([name] HIV Laboratory).

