6.16 Table 1. Table of Study Activities

Study Activity	V 1	V 2	V 3 ^c	V 3.5	V 4	V 5	V 6	V 7	V 8	V 9	V 10	V 11	V 12	V 13	V 14	V 15
Eligibility Screening	X															
Peripheral Neuropathy self-reported questionnaire	X		X		X	X	X	X	X	X	X	X	X		X	X
Informed consent	X															
Medical History	X		X		X	X	X	X	X	X	X	X	X		X	X
Concurrent meds	X															
Complete physical exam	X															
Brief physical exam			X		X	X	X	X	X	X	X	X	X		X	X
Vital Signs	X		X		X	X	X	X	X	X	X	X	X		X	X
CD4/CD8 T cell counts	X						X	X		X	X	X	X		X	X
HIV RNA Viral load	X							X		X	X	X	X		X	X
HIV Proviral DNA	X							X		X	X	X	X		X	X
CBC w/diff, platelet ^a	X		X		X	X	X	X	X	X	X	X	X	X	X	X
Heparin tubes for PBMC and plasma storage	X		X	X				X		X	X	X	X		X	
Serum chemistry ^b	X					X		X	X	X	X	X	X		X	X
Pre- and post-dose ixazomib level									X					X		
Adverse event evaluation					X	X	X	X	X	X	X	X	X		X	X
Urine Pregnancy test	X															
Leukapheresis		X												X		

a – Increased blood draw frequency may be required in the presence of hematologic toxicity. This will occur prior to each dose of ixazomib. In addition, increased blood draw frequency may be required if ixazomib is dosed weekly uninterrupted in Cycles 4-6.

b - Potassium, Creatinine, Alkaline phosphatase, ALT, AST, Total bilirubin, Direct bilirubin, Sodium, BUN, glucose, Chloride, Bicarbonate.

c- Visits 1 and 2 can occur on the same date, as long as they occur before visit 3.

6.17 Table 2: Instructions for treatment delays and dose reductions prior to ixazomib administration

CTCAE System/Organ/Class (SOC)	ADVERSE EVENT	AGENT	ACTION**
BASED ON INTERVAL ADVERSE EVENT			

CTCAE System/Organ/Class (SOC)	ADVERSE EVENT	AGENT	ACTION**
Investigations	Grade 2 thrombocytopenia (PLT count <75,000 - 50,000/mm ³) and/or neutropenia <1500 - 1000/mm ³	Ixazomib	Ixazomib dose should be omitted until the PLT and/or ANC has recovered to baseline values (counts >lower limit of normal). Ixazomib may be reinitiated at the same dose if the recovery has occurred in less than 7days. If the abnormality lasts ≥7 days or recurs, then the dose of ixazomib should be reduced by one dose level. If a patient is already at the lowest dose level, ixazomib should be permanently discontinued. Patients should have CBC checked weekly until resolution of abnormality.
	≥Grade 3 thrombocytopenia and/or neutropenia		Permanently discontinue ixazomib

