	≥Grade 2 increase in AST, ALT or total bilirubin	Ixazomib	Ixazomib dose should be omitted until the abnormal LFT has recovered to baseline values. Ixazomib may be reinitiated at the same dose if the recovery has occurred in less than 7days. If the abnormality lasts ≥7 days or recurs, then the dose of ixazomib should be reduced by one dose level. If a patient is already at the lowest dose level, ixazomib should be permanently discontinued. Patients should have LFTs checked weekly until resolution of abnormality.
Skin and subcutaneous tissue disorders	Any Grade ≤2 Rash	Ixazomib	Omit ixazomib until rash resolves. Restart at same dose. If the rash recurs, reduce dose by one dose level. If a patient is already at the lowest ixazomib dose, ixazomib should be permanently discontinued.
	Any rash, ≥Grade 3	Ixazomib	Ixazomib should be permanently discontinued.

CTCAE System/Organ/Class (SOC)	ADVERSE EVENT	AGENT	ACTION**
Nervous System Disorders	Grade 1 peripheral neuropathy	Ixazomib	Ixazomib should be permanently discontinued.
Other	Any Grade 3 AE (except if there is clear evidence that it is not ixazomib related – i.e. a plausible alternative reason).	Ixazomib	Permanently discontinue ixazomib.
	Grade 4 AE	Ixazomib	Permanently discontinue ixazomib
	Plasma HIV RNA >500copies/ml on 2 consecutive occasions. (except if there is clear evidence that it is not ixazomib related – i.e. a plausible alternative reason – for example missed ART doses).	Ixazomib	Permanently discontinue ixazomib. Perform HIV genotypic resistance testing.

Use the NCI Common Terminology Criteria for Adverse Events (CTCAE) version 4.0* unless otherwise specified for all Adverse Events.

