There is no interim analysis in this protocol, each cohort/dose level will be reviewed by the DSMB and decide upon escalation to the next dose level. This review will be conducted when all treated patients/cohort have received 4 weeks of treatment, or earlier if a DLT has occurred. Thereafter DSMB will review each cohort monthly.

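### Section 5.3 sets no minimum Cycle 1 exposure for a participant to count toward 0 of 3, so a level can be cleared on incomplete dosing, and the DLT definition that decides this is inconsistent

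*Combined protocol and SAP*

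**What the plan says.** Each of Groups 1 to 4 has three participants, with Cycle 1 doses planned on days 1, 8 and 15 (Section 5.2). Section 5.3 gives the escalation rule, "If no DLT are observed in 3 subjects, the next dosing level will be initiated", and the definition "The maximum tolerated dose is that level where no more than 0 out of 3 patients experience dose limiting toxicity". It requires the cohort to have completed 4 weeks, and elsewhere Cycle 1, but names no minimum number of doses. Section 7.3 defines a safety set (at least one dose) and a per-protocol set, but no DLT-evaluable set.

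The DLT definition appears in two places. Section 5.3 says "Dose limiting toxicities are defined in Section 6.17 Table 2". Section 6, under the neuropathy screening text, gives its own list, opening "The following toxicities will be considered to be dose limiting toxicities": Grade 4 or higher, Grade 3 unless clearly unrelated, and peripheral neuropathy from Grade 1.

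Table 2 sets dose actions and labels no row a DLT. For Grade 2 thrombocytopenia or neutropenia, and for liver-test rises from Grade 2, the dose is withheld until recovery. It is reduced one level if the abnormality lasts 7 days or more or recurs. At the bottom level, "If a patient is already at the lowest dose level, ixazomib should be permanently discontinued". For rash up to Grade 2: "Omit ixazomib until rash resolves. Restart at same dose", with a reduction on recurrence.

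Section 5.2, Section 7.2 (Interim Analysis) and Section 9.4.1 make opening the next level a DSMB decision. On timing, Section 7.2 says "This review will be conducted when all treated patients/cohort have received 4 weeks of treatment".

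**The concern.** A 0-of-3 rule is informative about a dose only to the extent that the three participants received that dose. Here exposure can fall because of toxicity, in participants who are already showing poor tolerance. If they still count as DLT-free, the level is cleared on less exposure than the rule implies, and the chance of clearing a level that is too toxic goes up. Five further participants are to be treated at the resulting maximum tolerated dose, and Section 1.5 expects that dose to inform later studies.

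The protocol already accepts the principle. Section 5.3 warns the DSMB that a group's toxicity may be understated if most of its members take NNRTIs that lower ixazomib exposure. It has no matching safeguard for exposure lost through withheld doses.

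**Working it through.** **The plan's own figure.** 4 groups × 3 + 5 = 17, the stated maximum. Section 7.1 bases the sample size on recruitment and gives no operating characteristics for escalation, so there is none to reproduce.

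**How little exposure can count.** Take a Group 2 or Group 3 participant with Grade 2 thrombocytopenia on the blood count before the day 8 dose (Section 6.4), still present before the day 15 dose (Section 6.5). Both doses are withheld, leaving 1 of 3, and the abnormality has lasted 7 days, so later dosing is one level lower. On the Section 6 list this is not a DLT. In Group 1 the same course ends treatment permanently, again without a DLT. Liver tests are first scheduled on treatment at the week 2 visit, so a rise found there costs only the day 15 dose.

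**Effect on the chance of 0 of 3.** Assume a true full-cycle DLT risk p that is the same for each participant, independence between participants, and equal risk per dose. Then:

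- Per-dose risk: d = 1 − (1 − p)^(1/3)
- All fully dosed: (1 − p)^3
- One participant with one dose: (1 − p)^2 × (1 − d)
- All three with one dose: (1 − d)^3 = 1 − p

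| p | d | Full dosing | One with one dose | All three with one dose |
|---|---|---|---|---|
| 0.20 | 0.072 | 0.512 | 0.594 | 0.800 |
| 0.30 | 0.112 | 0.343 | 0.435 | 0.700 |
| 1/3 | 0.126 | 0.296 | 0.388 | 0.667 |
| 0.40 | 0.157 | 0.216 | 0.304 | 0.600 |

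The direction does not depend on equal risk per dose, because fewer doses cannot raise the chance of observing a DLT. The size does depend on it.

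**How often a cohort is affected.** The documents give no Cycle 1 rate for these events. For an assumed rate q per participant, the chance that at least one of three is affected is 1 − (1 − q)^3: 0.271 at q = 0.10, 0.488 at 0.20 and 0.875 at 0.50. The range is an assumption.

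**Why the DLT definition matters.** Suppose the Table 2 events counted as DLTs, with q as an extra, non-overlapping rate. The chance of clearing a level would be (1 − p − q)^3. At p = 0.20 it falls from 0.512 to 0.343 at q = 0.10, and to 0.027 at q = 0.50. The two readings give very different escalation rules.

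**Review trigger.** Section 5.3 uses 4 weeks of follow-up and also completion of Cycle 1. Section 7.2 refers to 4 weeks of treatment received. A participant stopped in week 2 can meet the follow-up condition but, read literally, can never meet the one in Section 7.2.

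**The case against.** The strongest objection is that Section 5.3 itself refers to Table 2 for the DLT definition, and Table 2 contains these very rows. If Table 2 governs, the events may be DLTs and the level would not be cleared. This stands to the extent that the documents do not settle whether such participants are DLT-free. But Table 2 gives instructions on delays and reductions and labels nothing a DLT, and counting every row would make a Grade 1 rash dose-limiting, against the Section 6 list. The conflict has to be resolved either way.

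Second, escalation is described as a DSMB decision, a withdrawn participant may be replaced, and stopping ixazomib is a listed reason for withdrawal (Section 4.4.1). A reader might infer from the Section 5.3 sentence that Group 2 would open mechanically even if all of Group 1 had been stopped. The documents as a whole do not support that. What remains is that the automatic sentence contradicts the DSMB text, that replacement is optional, and that a participant who stays on study with omitted or reduced doses is not covered.

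Third, completing Cycle 1 and receiving 4 weeks of treatment could be read as exposure conditions, or all three triggers as simply day 28. Neither reading gives a number of doses.

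Fourth, figures are missing from Sections 5.2 and 5.3, and the DSMB charter is not among the documents. The finding concerns the visible text.

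**Conclusion.** The point holds in limited form. The visible text sets no minimum Cycle 1 exposure. On the Section 6 DLT list, participants with doses omitted or reduced for the named Grade 2 or lower events can count toward 0 of 3 after as little as one of three planned doses. Sections 5.3, 6 and 6.17 conflict on what a DLT is, the automatic sentence conflicts with the DSMB text, and the review triggers differ.

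The size is illustrative. At a true risk of 1/3, clearance rises from 30% to 39% with one participant cut to one dose; 67% is the extreme case. This rests on equal per-dose risk, which the documents do not establish.

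Three stronger readings are not supported:

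- A reader might infer that these participants never received the dose being cleared. Each takes at least the day 1 dose at the assigned level, so exposure is incomplete, not absent.
- A reader might infer that permanent stops for low-grade toxicity generally escape the DLT count. Peripheral neuropathy of Grade 1 or 2 is a DLT on the Section 6 list. For the other events Table 2 ends treatment only at the lowest level, essentially Group 1.
- A reader might infer from Section 1.4 that triggers are common. Its figures (rash about 50%, thrombocytopenia 34%) cover all grades in oncology patients and are not specific to Cycle 1.

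**What to change.** 1. Reconcile the DLT definition across Section 5.3, the list in Section 6 and Table 2. The sponsor must decide which events count; this review does not propose an answer.
2. State one review trigger and use it in both Section 5.3 and Section 7.2.
3. Apply the automatic 0-of-3 sentence and the maximum-tolerated-dose definition only when all three participants received every planned Cycle 1 dose at the assigned level and completed 4 weeks without a DLT.
4. In any other cohort, do not count a participant whose dosing was cut by toxicity as DLT-free, and do not drop or replace that participant silently. List each omitted, reduced or stopped Cycle 1 dose with its cause for the DSMB, and make escalation an explicit, recorded DSMB decision.

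Item 4 deliberately avoids calling such participants non-evaluable and replacing them as a matter of course. That would fill each cohort with people who tolerate the drug, and could exceed the maximum of 17, which 4 × 3 + 5 already uses in full. Replacement stays a DSMB option, to be checked against that maximum.

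No Table 2 action changes. The cost is protocol wording, one column in the DSMB listing and possibly a short delay for an affected cohort.

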5.4 Preparation and Administration of Study Drug

Preparation and storage

Ixazomib capsules, individually packaged in foil blister strips with child resistant paper backing (see below), will be stored unopened at 2-8°C (36-46°F). Of note, Ixazomib can be stored up to 40°C (104°F) for up to 30 days, and up to 50° (122°F) for up to 3 days). Study medication will be stored and dispensed by the Research Pharmacy at Mayo Clinic. Ixazomib that is dispensed to the patient for take-home dosing should remain in the blister packaging until the point of use. The investigative site will be providing the medication to the patient in units that comprise the correct dose configurations, which are prepackaged by the manufacturer. Capsules should remain in the blisters until the point of use. Comprehensive instructions will be provided to the patient in order to ensure compliance with dosing procedures. Patients will be instructed to store the medication in the refrigerator until the time of use.

Administration

All protocol-specific criteria for administration of ixazomib must be met and documented before drug administration. Ixazomib will be administered or dispensed only to eligible patients under the supervision of the investigator or identified subinvestigator(s). Patients should be monitored for toxicity, as necessary, and doses of ixazomib should be modified as needed to accommodate patient tolerance to treatment; this may include symptomatic treatment, dose interruptions, and adjustments of ixazomib dose. Capsules of ixazomib will also be referred to as study drug. Study drug will be supplied by Millennium as capsules of 0.5mg, 2.0mg, and 3.0mg, and 4.0mg ixazomib. Patients will be instructed to swallow ixazomib capsules whole, with water, and not to break, chew, or open the capsules. Ixazomib should be taken on an empty stomach (no food or drink) at least 1 hour before or 2 hours after a meal. Each capsule should be swallowed separately with a sip of water. A total of approximately 8 ounces (240 mL) of water should be taken with the capsules.

Missed doses can be taken as soon as the patient remembers if the next scheduled dose is 72 hours or more away. A double dose should not be taken to make up for a missed dose. If the patient vomits after taking a dose, the patient should not repeat the dose but should resume dosing at the time of the next scheduled dose.

5.5 Subject Compliance Monitoring

Reconciliation will occur accordingly when the patient returns for their next cycle of therapy. Any extremes in temperature should be reported as an excursion and will be managed on a case by case basis. Returned unused capsules should be discarded in a proper biohazard container.

5.6 Prior and Concomitant Therapy

See section 4.2 Exclusion criteria above.

5.7 Packaging

See section 5.4 above.

5.8 Receiving, Storage, Dispensing and Return

5.8.1 Receipt of Drug Supplies

Drug procurement: Investigational product will be supplied free of charge to trial participants by Takeda Pharmaceuticals, Inc.

5.8.2 Storage

See section 5.4 above.

5.8.3 Inventory/Dispensing/Labeling of Study Drug

See section 5.4. regarding storage of drug

A drug inventory/accountability log will be utilized to track study drug inventory/accountability. Upon shipment receipt, invoices will be verified and the inventory updated upon receipt. The inventory/accountability log will note name, dose, lot number, expiration, and quantity. A dispensing record will be tracked to note drug name, strength, quantity, lot number, drug expiration, patient name, date of dispensing.

Upon dispensing, a designated Research Pharmacist will label the medication with a label containing the following (Patient name, drug name/dose, dispense date, PI's name, address, telephone #, IRB #, directions for use, expiration date) and an auxiliary label noting "Caution-new drug limited by law to investigational use." The labeling and packaging will be double checked by an additional study team member prior to release to the patient. Counseling and drug information will be provided to the patient upon study drug dispensing.

Drug specific patient education/counseling

- Ixazomib capsules must be administered intact and should not be opened or manipulated in any way. Additionally, ixazomib capsules should remain in the blister packs until they are ready to be taken.
- Ixazomib should be taken on an empty stomach, at least 1 hour before or no sooner than 2 hours after a meal (as described in section 5.4 above).
- Thrombocytopenia has been observed with ixazomib. Patients will be instructed to report any unusual bruising or bleeding to the study team.
- GI side effects have been observed in patients treated with ixazomib (nausea, diarrhea, vomiting). If this should occur, patients should seek medical advice to ensure compliance with HIV ARV medications and effective management of the adverse event.
- Patients will be instructed to report any rash to study team.

- Patients will be instructed not to start any new medications or supplements without checking with the study team first. Our investigator team will assess patient's concomitant medications, including over the counter and supplements. Ixazomib is metabolized through both CYP enzymes and non-CYP proteins, and drug to drug interactions exist with strong inducers of CYP3A.
- The NNRTIs etravirine and efavirenz are moderate CYP3A enzyme inducers and have potential to decrease systemic exposure to ixazomib. That possibility will be explored by measuring trough ixazomib levels in all patients and comparing ixazomib concentrations in patients on different ART regimens.

